5.3. Number of Participants

Approximately 14 healthy subjects (to achieve 12 completed subjects) will participate in Part 1 of the study, and approximately 24 subjects (to achieve 18 evaluable subjects) will participate in Part 2 of the study. A subject will participate in only one part of the study. If participants prematurely discontinue the study for reasons other than AE, additional

replacement participants may be assigned to the same treatment group sequence at the discretion of the Sponsor in consultation with the investigator.

5.4. Participant and Study Completion

A completed subject is one who has completed all phases of the study including the follow-up visit.

The end of the study is defined as the last subject's last visit.

5.5. Scientific Rationale for Study Design

This open-label, randomized, cross-over design is well-established for the evaluation of relative bioavailability of different oral dosage forms. Randomization of the treatment sequences is an attempt to prevent bias. The washout of 7 days between dosing periods should eliminate the possibility of carryover of drug exposure from the previous dosing period. In each part of the study, there are appropriately named "test" and "reference" study treatments which will be evaluated for the relative bioavailability comparisons.

The study is subject to the appropriate regulatory approval and Ethics Committee approval, and will be listed on the website ClinicalTrials.gov. No blinding or placebo control will be used, as these are not necessary for the purposes of this study.

5.6. Dose Justification

The US Food and Drug Administration (FDA)-approved dose of DTG for treatment-naïve HIV-infected adult and pediatric patients 12 years and older (and ≥ 40 kilogram [kg]) is 50 mg once daily. The adult dose is given as 1x50 mg tablet once daily.

Part 1 of the study will compare relative BA of five 10-mg conventional tablets (test) to that of one 50-mg conventional tablet (reference). For part 1, the approved adult dose of 50 mg DTG conventional tablet is used as a reference to benchmark exposures with paediatric formulations to what is safe and effective in adults.

Part 2 of the study will compare relative BA of five 5 mg dispersible tablets administered as "disperse and immediately take" and of dispersible 5 mg tablets to be administered as "direct to mouth" to that of a single 25 mg conventional tablet (reference) administered direct to mouth. The 25 mg dose of DTG control dose used in Part 2 of this study will accommodate the relative BA assessment of the two pediatric dosage forms and will require a dosing of only five (5) 5 mg tablets, as opposed to 10 tablets that would have been necessary if the 50 mg DTG control dose would have been chosen for evaluation in Part 2 of the study. With respect to reference dose in Part 2 of this study, the 25 mg tablet is quantitatively proportional to the 50 mg tablet and hence two 25mg tablets are equivalent to 50 mg tablet. However, the 25 mg tablet was chosen as a comparator for this part so as to decrease the burden on the subjects to consume 10 x 5 mg tablets directly to mouth as well as to minimize any associated variability.

6. STUDY POPULATION

Prospective approval of protocol deviations to recruitment and enrolment criteria, also known as protocol waivers or exemptions, is not permitted.

Deviations from inclusion and exclusion criteria are not allowed because they can potentially jeopardize the scientific integrity of the study, regulatory acceptability or subject safety. Therefore, adherence to the criteria as specified in the protocol is essential.

Specific information regarding warnings, precautions, contraindications, adverse events, and other pertinent information on the ViiV Healthcare investigational product or other study treatment that may impact subject eligibility is provided in the Investigator's Brochure (see GlaxoSmithKline Document Number [RM2007/00683/10](#)).

6.1. Inclusion Criteria

Specific information regarding warnings, precautions, contraindications, adverse events, and other pertinent information on the ViiV Healthcare investigational product or other study treatment that may impact subject eligibility is provided in the Investigator's Brochure [GlaxoSmithKline Document Number [RM2007/00683/10](#)].

Participants are eligible to be included in the study only if all of the following criteria apply:

AGE
1. Between 18 and 65 years of age inclusive, at the time of signing the informed consent.
TYPE OF SUBJECT AND DIAGNOSIS INCLUDING DISEASE SEVERITY
2. Healthy as determined by the investigator or medically qualified designee based on a medical evaluation including medical history, physical examination, laboratory tests and cardiac evaluation (history and electrocardiogram [ECG]). A subject with a clinical abnormality or laboratory parameter(s) which is/are not specifically listed in the inclusion or exclusion criteria, outside the reference range for the population being studied may be included only if the investigator in consultation with the Medical Monitor agree and document that the finding is unlikely to introduce additional risk factors and will not interfere with the study procedures.
WEIGHT
3. Body weight ≥ 50 kg for males and ≥ 45 kg for females and body mass index (BMI) within the range $18.5 - 31.0$ kg/m^2 (inclusive)
SEX
4. Male or female a. Non-reproductive potential defined as:


 • Pre-menopausal females with one of the following: 
 • Documented tubal ligation • Documented hysteroscopic tubal occlusion procedure with follow-up confirmation of bilateral tubal occlusion • Hysterectomy • Documented Bilateral Oophorectomy • Postmenopausal defined as 12 months of spontaneous amenorrhea [in questionable cases a blood sample with simultaneous follicle stimulating hormone (FSH) and estradiol levels consistent with menopause (refer to laboratory reference ranges for confirmatory levels)]. Females on hormone replacement therapy (HRT) and whose menopausal status is in doubt will be required to use one of the highly effective contraception methods if they wish to continue their HRT during the study. Otherwise, they must discontinue HRT to allow confirmation of post-menopausal status prior to study enrolment. 
b. Reproductive potential and agrees to follow one of the options listed in the Modified List of Highly Effective Methods for Avoiding Pregnancy in Females of Reproductive Potential (FRP) (see Appendix 5 [Section 12.5]) from 30 days prior to the first dose of study medication and until 2 weeks after dosing with study medication and completion of the follow-up visit.

The investigator is responsible for ensuring that subjects understand how to properly use these methods of contraception.

INFORMED CONSENT

5. Capable of giving signed informed consent as described in Section 12.3, which includes compliance with the requirements and restrictions listed in the consent form and in this protocol.

6.2. Exclusion Criteria

Participants are excluded from the study if any of the following criteria apply:

CONCURRENT CONDITIONS/MEDICAL HISTORY (INCLUDES LIVER FUNCTION AND QT DURATION CORRECTED FOR HEART RATE [QTc] INTERVAL)

1. ALT and bilirubin $>1.5 \times \text{ULN}$ (isolated bilirubin $>1.5 \times \text{ULN}$ is acceptable if bilirubin is fractionated and direct bilirubin $<35\%$).
2. Current or chronic history of liver disease, or known hepatic or biliary abnormalities (with the exception of Gilbert's syndrome or asymptomatic gallstones).
3. QT correction using Fridericia Formula (QTcF) >450 Milliseconds (msec)

NOTES:

- The QTcF is the QT interval corrected for heart rate according to Fridericia's formula (QTcF), machine-read or manually over-read.

- The specific formula that will be used to determine eligibility and discontinuation for an individual subject should be determined prior to initiation of the study. In other words, several different formulae cannot be used to calculate the QTc for an individual subject and then the lowest QTc value used to include or discontinue the subject from the trial.
- For purposes of data analysis, QTcF, will be used as specified in the Reporting and Analysis Plan (RAP).

CONCOMITANT MEDICATIONS

4. Unable to refrain from the use of prescription (i.e., or non-prescription drugs, including vitamins, herbal and dietary supplements (including St John's Wort) within 7 days (or 14 days if the drug is a potential enzyme inducer) or 5 half-lives (whichever is longer) prior to the first dose of study medication, unless in the opinion of the Investigator and ViiV Medical Monitor the medication will not interfere with the study procedures or compromise subject safety.

RELEVANT HABITS

5. History of regular alcohol consumption within 6 months of the study defined as:
 - An average weekly intake of >14 drinks for males or >7 drinks for females. One drink is equivalent to 12 g of alcohol: 12 ounces (360 milliliters [mL]) of beer, 5 ounces (150 mL) of wine or 1.5 ounces (45 mL) of 80 proof distilled spirits.
6. Urinary cotinine levels indicative of smoking or history or regular use of tobacco- or nicotine-containing products within 1 month prior to screening.

CONTRAINdicATIONS

7. History of sensitivity to any of the study medications, or components thereof or a history of drug or other allergy that, in the opinion of the investigator or Medical Monitor, contraindicates their participation.

DIAGNOSTIC ASSESSMENTS AND OTHER CRITERIA

8. Creatinine clearance (CrCL) <90 mL/min
9. A positive hepatitis B surface antigen (HBsAg) or a positive hepatitis B core antibody with a negative hepatitis B surface antibody, positive hepatitis C antibody test result at screening or within 3 months prior to first dose of study treatment.
10. A positive pre-study drug/alcohol screen.
11. A positive test for HIV antibody.
12. Where participation in the study would result in donation of blood or blood product in excess of 500 mL within 56 days.
13. The subject has participated in a clinical trial and has received an investigational product within the following time period prior to the first dosing day in the current study: 30 days, 5 half-lives or twice the duration of the biological effect of the investigational product (whichever is longer).
14. Exposure to more than four new chemical entities within 12 months prior to the first dosing day.

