3.3.1. Risk Assessment

Potential Risk of Clinical Significance	Data/Rationale for Risk	Mitigation Strategy ^a
	Refer to Investigator Brochure (IB) for additional information	
Hypersensitivity reaction (HSR) and rash	HSR has been observed uncommonly with DTG. Rash was commonly reported in DTG Phase IIb/III clinical trials; episodes were generally mild to moderate in intensity; no episodes of severe rash, such as Stevens-Johnson Syndrome (SJS), Toxic Epidermal Necrolysis (TEN) and erythema multiforme were reported.	
 Subjects with history of allergy/sensitivity to any of the study drugs are excluded (Section 6.2) Specific/detailed toxicity management guidance is provided for HSR and rash (Section 12.7). For Grade 3/4 rash, subjects must permanently discontinue study drug and be withdrawn from the study (Section 12.7.4) The subject informed consent form includes information on this risk and the actions subjects should take in the event of an HSR or associated signs and symptoms.
Drug induced liver injury (DILI) and other clinically significant liver chemistry elevations	Non-clinical data suggested a possible, albeit low, risk for hepatobiliary toxicity with DTG. Drug-related hepatitis is considered an uncommon risk for antiretroviral therapy (ART) containing DTG regardless of dose or treatment population. For subjects with hepatitis B virus (HBV) and/or hepatitis C virus (HCV) co-infection, improvements in immunosuppression as a result of HIV virologic and immunologic responses to DTG-containing ART, along with inadequate therapy for HBV co-infected subjects, likely contributed to significant elevations in liver chemistries.	
Subjects meeting either of the following criteria during the screening period are excluded (Section 6.2).
 
 Current or chronic history of liver disease, or known hepatic or biliary abnormalities (with the exception of Gilbert's syndrome or asymptomatic gallstones). Alanine Aminotransferase (ALT) or bilirubin >1.5x upper limit of normal (ULN). Subjects positive for HBV (hepatitis B virus surface antigen positive [+HBsAg] or positive hepatitis B core antibody with a negative HBsAg), or HCV (positive hepatitis C antibody test) within 3 months of the Day 1 study visit. 
Specific/detailed liver stopping criteria and toxicity management guidance is provided for suspected DILI or other clinically significant liver chemistry elevations (Section 12.2).

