9.3.4. Clinical Safety Laboratory Assessments

All protocol required laboratory assessments, as defined in [Table 5](#), must be conducted in accordance with the Laboratory Manual, and Protocol Time and Events Schedule in the SoA for the timing and frequency. Laboratory requisition forms must be completed and samples must be clearly labelled with the subject number, protocol number, site/centre number, and visit date. Reference ranges for all safety parameters will be provided to the site by the laboratory responsible for the assessments.

If additional non-protocol specified laboratory assessments are performed at the institution's local laboratory and result in a change in subject management or are considered clinically significant by the investigator (e.g., SAE or AE or dose modification) the results must be recorded in the eCRF.

Refer to the Study Reference Manual (SRM)/BioPacket for appropriate processing and handling of samples to avoid duplicate and/or additional blood draws.

Haematology, clinical chemistry, urinalysis and additional parameters to be tested are listed in [Table 5](#).

Table 5 Protocol Required Safety Laboratory Assessments

Laboratory Assessments	Parameters			
Haematology	Platelet Count	RBC Indices		White blood cell (WBC) count with Differential:
	Hematocrit	Mean corpuscular hemoglobin (MCH) Mean corpuscular volume (MCV)		Neutrophils
	Hemoglobin			Lymphocytes
	Red blood cell Count (RBC)			Monocytes
	WBC Count (absolute)			Eosinophils Basophils
Clinical Chemistry ^a	Blood urea nitrogen (BUN)	Potassium	AST (serum glutamic oxaloacetic transaminase [SGOT])	Total and direct bilirubin
	Creatinine	Sodium	ALT (serum glutamic pyruvic transaminase [SGPT])	Total Protein
	Glucose	Calcium	Alkaline phosphatase	Albumin
	Creatine phosphokinase (CPK)			
Routine Urinalysis	
 Specific gravity pH, glucose, protein, blood and ketones by dipstick Microscopic examination (if blood or protein is abnormal) 			

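### Exclusion criterion 1 joins ALT and bilirubin with 'and', so read literally it does not exclude an isolated ALT above 1.5 x ULN, although Section 3.3.1 relies on 'or'

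*Protocol*

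**What the plan says.** The list in Protocol Section 6.2 opens with "Participants are excluded from the study if any of the following criteria apply". Its first item is "ALT and bilirubin $>1.5 \times \text{ULN}$ (isolated bilirubin", and the parenthesis goes on to say that isolated bilirubin above 1.5 x ULN "is acceptable if bilirubin is fractionated and direct bilirubin" is below 35%. Nothing is said about an isolated ALT elevation.

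Section 3.3.1 lists the mitigations for drug-induced liver injury. It introduces them with "Subjects meeting either of the following criteria during the screening period are excluded (Section 6.2" and gives the laboratory limit as "Alanine Aminotransferase (ALT) or bilirubin >1.5x upper limit of normal (ULN".

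Both are current text and use the same 1.5 x ULN threshold. They differ in the conjunction and in the bilirubin exception, which Section 3.3.1 omits.

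**The concern.** Section 3.3.1 attributes to Section 6.2 a rule that Section 6.2, taken literally, does not contain. The word *any* in the lead-in to 6.2 operates between the numbered criteria. It does not change the *and* inside criterion 1, and that word decides whether a raised ALT excludes on its own.

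Section 6 forbids waivers of the eligibility criteria and requires them to be followed as written. A criterion applied on those terms should have one reading. Here a site could enrol a healthy volunteer with, say, ALT at 2 x ULN and normal bilirubin without breaching criterion 1, although the risk assessment presents that exclusion as a safeguard. Section 3.3.2 expects no benefit to these volunteers from dosing, so the entry limit should be unambiguous.

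**Working it through.** No sample-size or power figure is involved. The check compares the two sections for each liver-test pattern and then looks for any other ALT limit.

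**Step 1: is the subject excluded?** *Raised* means above 1.5 x ULN.

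| Pattern | 3.3.1 | 6.2, literal *and* | 6.2, *each of* ALT and bilirubin |
|---|---|---|---|
| ALT raised, bilirubin not | Yes | **No** | Yes |
| Bilirubin raised, ALT not, direct <35% | Yes (exception omitted) | No | No (exception) |
| Bilirubin raised, ALT not, direct 35% or more | Yes | No on a strict *and*, though the parenthesis implies yes | Yes |
| Both raised | Yes | Yes | Yes |

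The first row is the safety conflict. In the second row Section 3.3.1 is merely stricter than 6.2, which leaves no safety gap. The third row shows why the strict reading cannot be what was meant: if both elevations were needed, isolated bilirubin would never exclude and the exception would have no function.

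**Step 2: does anything else supply the ALT limit?**

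- The remaining inclusion and exclusion criteria contain no numeric ALT threshold. Exclusion 2 is qualitative (liver disease or a known hepatic or biliary abnormality).
- Inclusion 2 requires the investigator to consider the subject healthy, laboratory tests included. Its further step, documented agreement with the Medical Monitor on out-of-range findings, covers parameters "which is/are not specifically listed in the inclusion or exclusion criteria". Because ALT is named in exclusion 1, it is arguable whether that step applies to an isolated ALT. Neither part of inclusion 2 sets a figure of 1.5 x ULN.
- Sections 8.1.1 and 12.2 stop treatment at ALT of 3 x ULN or more. That is an on-study treatment rule and does not govern entry.

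**Step 3: how wide is the gap?**

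- From the entry limit to the stopping threshold: 3.0 / 1.5 = 2, a two-fold range of isolated ALT with no numeric limit under the literal reading.
- The grading table in Appendix 6 (Section 12.6) puts ALT of 1.25 to <2.5 x ULN at Grade 1 and 2.5 to <5.0 x ULN at Grade 2. The upper part of the gap, 2.5 to <3 x ULN, is therefore already Grade 2, the level from which SAP Sections 2.1 and 8.1 list laboratory toxicities.
- Planned enrolment (Section 5.3): 14 + 24 = 38.
- Planned exposure per subject (Section 5.2): Part 1, 2 x 50 mg = 100 mg; Part 2, 3 x 25 mg = 75 mg, with doses at least 7 days (-4 h) apart.
- Monitoring: Table 5 in Section 9.3.4 includes "ALT (serum glutamic pyruvic transaminase [SGPT", and Table 2 schedules laboratory tests on Day -1 and after dosing in each period.

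**The case against.** The best case for leaving the text alone is that criterion 1 explains itself. Reading it as *each of ALT and bilirubin* gives every word a function, makes the isolated-bilirubin exception meaningful and agrees with Section 3.3.1. On that view the protocol has one loosely worded statement and one clear one, linked by a cross-reference.

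The objection also holds that unchecked entry is hard to reach. If isolated ALT counts as listed in criterion 1, the subject is excluded. If it does not, inclusion 2 calls for documented agreement with the Medical Monitor on any value outside the reference range, which is a tighter trigger than 1.5 x ULN.

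Much of this stands. The intended meaning can be recovered, many sites would apply it, and entry would still involve clinical judgement. It also follows that the enrolment and exposure figures describe the setting and do not measure harm. Little weight should go to the contrast with criterion 9 ("A positive hepatitis B surface antigen (HBsAg) or a positive hepatitis B core antibody"), which does use *or* but is itself loosely punctuated.

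The objection does not remove the mismatch. Section 6.2 is the text that sites must follow, its literal reading contradicts the mitigation that cites it, and a discretionary step does not replace a stated limit.

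**Conclusion.** The concern holds, as a minor point. Criterion 1 is wrong as written: taken literally, it lets in a volunteer with isolated ALT above 1.5 x ULN, whom Section 3.3.1 says is excluded, and no other criterion supplies the limit. It is a wording error and not a design choice.

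The practical consequence is bounded by the repeat ALT tests, the stopping rule at 3 x ULN and the two or three single doses. The number of volunteers affected cannot be estimated from the documents. The conclusion depends only on the protocol's wording and on no assumption about ALT values in the screened population. It has no bearing on the sample size or on the PK comparisons.

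**What to change.** Reword Section 6.2, criterion 1, as two alternatives: *ALT >1.5 x ULN; or bilirubin >1.5 x ULN, except that an isolated bilirubin elevation is allowed when fractionation shows direct bilirubin <35%.* Keep the 1.5 x ULN threshold, which both sections share. For consistency only, add the same bilirubin exception to Section 3.3.1.

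The cost is one line in each section. There may be a few more screen failures, but only at a site that would otherwise have used the literal reading; the number cannot be estimated from the documents.

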6.3. Lifestyle Restrictions

6.3.1. Meals and Dietary Restrictions

Refrain from consumption of red wine, Seville oranges, grapefruit or grapefruit juice [and/or pummelos, exotic citrus fruits, grapefruit hybrids or fruit juices] from 7 days prior to the first dose of study medication until after the final dose.

Once in the clinical unit, subjects will not be allowed to eat anything other than the food provided by the study center.

6.3.2. Fasting Conditions

During the overnight period from Day -1 to Day 1 of each dosing period:

- An evening meal and/or snack will be provided by the unit (e.g. on Day -1).
- Subjects must then fast from all food and drink (except water) for 10 hrs pre-dose and prior to any clinical laboratory evaluations (except repeat evaluations).
- Water is permitted with dosing (200-250 mL) for all Treatments except Treatment C and at all times except 1 hour (hr) pre-dose through 2-hrs post-dose.
- No food is allowed for at least 4 hrs post-dose.

6.3.3. Fed Conditions

With the exception of the time period outlined for fasting conditions, subjects will receive all other meals as defined as standard for the study center.

6.3.4. Caffeine, Alcohol, and Tobacco

During each treatment period, subjects will abstain from ingesting caffeine- or xanthine-containing products (e.g., coffee, tea, cola drinks and chocolate) for 24 hrs prior to the start of dosing until collection of the final PK and or pharmacodynamic sample during each session.

During each dosing session, subjects will abstain from alcohol for 24 hrs prior to the start of dosing until collection of the final pharmacokinetic and or pharmacodynamic sample during each session.

Use of tobacco products is not allowed from 1 month prior to screening and until after the final follow-up visit.

6.3.5. Activity

Subjects will abstain from strenuous exercise for 48 hrs prior to each blood collection for clinical laboratory tests. Subjects may participate in light recreational activities during studies (e.g., watch television, read).

6.4. Screen Failures

Screen failures are defined as participants who consent to participate in the clinical study but are not subsequently randomized/entered in the study. A minimal set of screen failure

information is required to ensure transparent reporting of screen failure participants to meet the Consolidated Standards of Reporting Trials (CONSORT) publishing requirements and to respond to queries from regulatory authorities. Minimal information includes demography, screen failure details, eligibility criteria, and any serious adverse events (SAEs).

Individuals who do not meet the criteria for participation in this study (screen failure) may not be rescreened.

